5.2.3 Reporting Procedure

This study requires that expedited adverse event reporting use CTEP's Adverse Event Reporting System (CTEP-AERS). The CTEP's guidelines for CTEP-AERS can be found at <http://ctep.cancer.gov>. A CTEP-AERS report must be submitted electronically to ECOG-ACRIN and the appropriate regulatory agencies via the CTEP-AERS Web-based application located at <http://ctep.cancer.gov>.

In the rare event when Internet connectivity is disrupted a 24-hour notification is to be made by telephone to

- the AE Team at ECOG-ACRIN [contact])
- the FDA ([name])

An electronic report MUST be submitted immediately upon re-establishment of internet connection.

Supporting and follow up data: Any supporting or follow up documentation must be uploaded to the Supplemental Data Folder in Medidata Rave within 48-72 hours. In addition, supporting or follow up

documentation must be faxed to the FDA [contact]) in the same timeframe.

CTEP Technical Help Desk: For any technical questions or system problems regarding the use of the CTEP-AERS application, please contact the NCI Technical Help Desk at [contact] or by phone at [name].

[figure not shown]
5.2.4 Determination of Reporting Requirements

Many factors determine the reporting requirements of each individual protocol, and which events are reportable in an expeditious manner, including:

- the phase (0, 1, 2, or 3) of the trial
- whether the patient has received an investigational or commercial agent or both
- the Common Terminology Criteria for Adverse Events (CTCAE) grade
- the relationship to the study treatment (attribution)
- the expectedness of the adverse event

Using these factors, the instructions and tables in the following sections have been customized for protocol EA2142 and outline the specific expedited adverse event reporting requirements for study EA2142.

5.2.5 Steps to determine if an event is to be reported in an expedited manner

5.2.6 Expedited Reporting Requirements for Arms A and B on protocol EA2142

Commercial Agents: Capecitabine, Temozolomide, Cisplatin, Carboplatin, and Etoposide

Expedited reporting requirements for adverse events experienced by patients on arm(s) with commercial agents only – Arms A and B

Attribution	Grade 4		Grade 5 ^a		ECOG-ACRIN and Protocol-Specific Requirements
	Unexpected	Expected	Unexpected	Expected	
Unrelated or Unlikely			7 calendar days	7 calendar days	See footnote (b) for special requirements.
Possible, Probable, Definite	7 calendar days		7 calendar days	7 calendar days	

7 Calendar Days: Indicates a full CTEP-AERS report is to be submitted within 7 calendar days of learning of the event.

Rev. Add3

a A death occurring while on study or within 30 days of the last dose of treatment requires both routine and expedited reporting, regardless of causality. Attribution to treatment or other cause must be provided.

NOTE: A death due to progressive disease should be reported as a Grade 5 “Disease progression” under the System Organ Class (SOC) “General disorder and administration site conditions”. Evidence that the death was a manifestation of underlying disease (e.g. radiological changes suggesting tumor growth or progression: clinical deterioration associated with a disease process) should be submitted.

NOTE: Any death that occurs > 30 days after the last dose of treatment and is attributed possibly, probably, or definitely to the treatment must be reported within 7 calendar days of learning of the event.

b Protocol-specific expedited reporting requirements: The adverse events listed below also require expedited reporting for this trial:

Serious Events: Any event following treatment that results in persistent or significant disabilities/incapacities, congenital anomalies, or birth defects must be reported via CTEP-AERS within 7 calendar days of learning of the event. For instructions on how to specifically report these events via CTEP-AERS, please contact the AEMD Help Desk at [contact] or [contact]. This will need to be discussed on a case-by-case basis.

5.2.7 Other recipients of adverse event reports and supplemental data

ECOG-ACRIN will forward CTEP-AERS reports to the appropriate regulatory agencies and pharmaceutical company, if applicable.

Adverse events determined to be reportable via CTEP-AERS must also be reported by the institution, according to the local policy and procedures, to the Institutional Review Board responsible for oversight of the patient.

5.2.8 Second Primary Cancer Reporting Requirements

All cases of second primary cancers, including acute myeloid leukemia (AML) and myelodysplastic syndrome (MDS), that occur following treatment on NCI-sponsored trials must be reported to ECOG-ACRIN using Medidata Rave

- **A second malignancy is a cancer that is UNRELATED to any prior anti-cancer treatment (including the treatment on this protocol). Second malignancies require ONLY routine reporting as follows:**
 1. Complete a Second Primary Form in Medidata Rave within 14 days.
 2. Upload a copy of the pathology report to ECOG-ACRIN via Medidata Rave confirming the diagnosis.
 3. If the patient has been diagnosed with AML/MDS, upload a copy of the cytogenetics report (if available) to ECOG-ACRIN via Medidata Rave.
- **A secondary malignancy is a cancer CAUSED BY any prior anti-cancer treatment (including the treatment on this protocol). Secondary malignancies require both routine and expedited reporting as follows:**
 1. Complete a Second Primary Form in Medidata Rave within 14 days.
 2. Report the diagnosis via CTEP-AERS at <http://ctep.cancer.gov>
Report under a.) leukemia secondary to oncology chemotherapy, b.) myelodysplastic syndrome, or c.) treatment related secondary malignancy
 3. Upload a copy of the pathology report to ECOG-ACRIN via Medidata Rave and submit a copy to NCI/CTEP confirming the diagnosis.
 4. If the patient has been diagnosed with AML/MDS, upload a copy of the cytogenetics report (if available) to ECOG-ACRIN via Medidata Rave and submit a copy to NCI/CTEP.

NOTE: The ECOG-ACRIN Second Primary Form and the CTEP-AERS report should not be used to report recurrence or development of metastatic disease.

NOTE: If a patient has been enrolled in more than one NCI-sponsored study, the ECOG-ACRIN Second Primary Form must be submitted for the most recent trial. ECOG-ACRIN must be provided with a copy of the form and the associated pathology report and cytogenetics report (if available) even if ECOG-ACRIN was not the patient's most recent trial.

NOTE: Once data regarding survival and remission status are no longer required by the protocol, no follow-up data should be submitted via CTEP-AERS or by the ECOG-ACRIN Second Primary Form.

5.3 Dose Modifications

5.3.1 General

Dose reductions will be based on current dose. If dose reduction is required, reduction is permanent. Missed doses will not be made up. No dose escalation is permitted for any of the study drugs.

Dose will be modified for all drugs if there is $\geq 10\%$ change in patient's weight while on study. For oral agents, particularly capecitabine, a new dose calculation may result in the same number of pills to be administered due to rounding issues.

Doses will be determined according to (1) non-hematologic AEs during the previous cycle, as well as (2) the lowest ANC and platelet counts during that cycle.

Patients may receive **a maximum of two** dose reductions per agent. If a third reduction is required, the patient should discontinue all protocol treatment. However, for Arm A, patients may discontinue one agent due to toxicity and continue the other on-study.

If different percentages of dose reductions for a specific drug are required because of two different types of toxicities, the greater percentage dose reduction should be undertaken.

AEs determined to be unrelated to study treatment will not require dose reduction.

NOTE: If patients have been off study treatment ≥ 4 weeks of next planned cycle start date, patients must discontinue protocol treatment.

NOTE: Starting cycles early is prohibited due to safety purposes.

All toxicity grades below are described using the NCI Common Terminology Criteria for Adverse Events (CTCAE) version 4.0.

All appropriate treatment areas should have access to a copy of the CTCAE version 4.0. A copy of the CTCAE version 4.0 can be downloaded from the CTEP website (<http://ctep.cancer.gov>).

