5.3.3 Temozolomide Dose Modifications

- **Dose reductions:** For non-hematologic grade 3 and 4 AEs (except for nausea and vomiting as well as AEs unrelated to treatment) the dose should be reduced according to the Temozolomide Dose Level Table at the discretion of the investigator. Dose reductions for treatment day ANC and platelet counts should also be made according to the Dose Level Table below. Each dose reduction will be a 20% reduction from the prior level.
- **Discontinuation:** Also, except for nausea and vomiting, if any of the same non-hematologic grade 3 and 4 AEs that are at least possibly related to temozolomide recur after two reductions for that AE, then temozolomide will be stopped.

Temozolomide Dose Level Table	
Dose Level	Dose in mg/m ²
0	200
-1	160
-2	128

*Note this is a 20% dose reduction with each dose level.

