5.3.3.1 Hematologic Toxicity

ANC (/mm ³)		Platelets (/mm ³)	% of Planned Temozolomide
≥ 1500/mm ³	and	≥ 100,000/mm ³	100%
750-1499/mm ³	or	50,000-99,999/mm ³	Hold*
< 750/mm ³	or	< 50,000/mm ³	Hold**

* Upon recovery to ANC ≥ 1,500/mm³ and platelets to ≥ 100,000/mm³, the dose level -1 will be administered (160 mg/m²). Discontinue temozolomide dose if patients do not recover within ≤ 3 weeks. If patient was already receiving Temozolomide at the -1 dose level, reduce to the -2 dose (128 mg/m²).

** Upon recovery to ANC ≥ 1,500/mm³ and platelets to ≥ 100,000/mm³, the dose level -2 will be administered (128 mg/m²). Discontinue dose if patients do not recover within ≤ 3

weeks. If patient was already receiving Temozolomide at the -2 dose level, temozolomide should be discontinued.

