5.3.4.1 Recommended Dose Modifications

Worst Toxicity CTCAE v4.0 Grade (unless otherwise specified)	Recommended Dose Modifications to cisplatin any time during a cycle of therapy	Recommended Dose Modifications to carboplatin any time during a cycle of therapy
BLOOD AND LYMPHATIC SYSTEM DISORDER		
Anemia		
Grade 1 (Hgb < LLN-10.0 g/dL)	Maintain dose level.	Maintain dose level.
Grade 2 (Hgb < 10.0 g/dL - 8.0 g/dL)	Maintain dose level.	Maintain dose level.
Grade 3 (Hgb < 8.0 g/dL); transfusion indicated	Maintain dose level.	Maintain dose level.
Grade 4 (Life threatening consequences; urgent intervention indicated); related to study drugs	Discontinue study treatment.	Discontinue study treatment.
ANC decreased (Neutropenia)		
Grade 1 (ANC < LLN - 1.5 x 10 ⁹ /L)	Maintain dose level.	Maintain dose level
Grade 2 (ANC < 1.5 - 1.0 x 10 ⁹ /L)	Maintain dose level.	Maintain dose level
Grade 3 (ANC < 1.0 - 0.5 x 10 ⁹ /L)	Omit dose of cisplatin until resolved to CTCAE Grade ≤ 1, and no fever. Then: - If resolved in ≤ 7 days, then maintain dose level - If resolved in > 7 days, then maintain dose level and consider prophylactic growth factor support per ASCO guidelines - If second occurrence, then ↓ 1 dose level for subsequent cycles.	Omit dose of carboplatin until resolved to CTCAE Grade ≤ 1, and no fever. Then: - If resolved in ≤ 7 days, then maintain dose level - If resolved in > 7 days, then maintain dose level and initiate prophylactic growth factor support per ASCO guidelines - If second occurrence, then ↓ 1 dose level for subsequent cycles.
Grade 4 (ANC < 0.5 x 10 ⁹ /L)	Omit dose of cisplatin until resolved to CTCAE ≤ Grade 1, then ↓ 1 dose level; additionally, consider prophylactic growth factor support per ASCO guidelines.	Omit dose of carboplatin until resolved to CTCAE ≤ Grade 1, then ↓ 1 dose level; additionally, consider prophylactic growth factor support per ASCO guidelines.
Febrile neutropenia		

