Grade 3 (ANC < 1.0 x 10 ⁹ /L, single temperature of > 38.3°C or a sustained temperature of ≥ 38.0°C)	Omit dose of cisplatin, then - If resolved by ≤ 7 days, then ↓ 1 dose level and consider prophylactic growth factor support per ASCO guidelines. - If not resolved within 7 days despite appropriate management including full clinically indicated course of antibiotics, if indicated, discontinue patient from study treatment.	Omit dose of carboplatin, then - If resolved by ≤ 7 days, then ↓ 1 dose level and consider prophylactic growth factor support per ASCO guidelines. - If not resolved within 7 days despite appropriate management including full clinically indicated course of antibiotics, if indicated, discontinue patient from study treatment.
Grade 4	Discontinue study treatment.	Discontinue study treatment.
Platelet count decreased (Thrombocytopenia)		
Grade 1 (PLT < LLN - 75 x 10 ⁹ /L)	Omit dose of cisplatin until resolved to CTCAE Grade ≤ 1, then maintain dose level	Omit dose of carboplatin until resolved to CTCAE Grade ≤ 1, then maintain dose level
Grade 2 (PLT < 75 - 50 x 10 ⁹ /L)	Omit dose of cisplatin until resolved to CTCAE Grade ≤ 1, then ↓ 1 dose level	Omit dose of carboplatin until resolved to CTCAE Grade ≤ 1, then ↓ 1 dose level
Grade 3 (PLT < 50 - 25 x 10 ⁹ /L)	Omit dose of cisplatin until resolved	Omit dose of carboplatin until

Worst Toxicity CTCAE v4.0 Grade (unless otherwise specified)	Recommended Dose Modifications to cisplatin any time during a cycle of therapy	Recommended Dose Modifications to carboplatin any time during a cycle of therapy
	to CTCAE Grade \leq 1, then - If resolved in \leq 7 days, then then ↓ 1 dose level. - If resolved in $>$ 7 days, then discontinue study treatment.	resolved to CTCAE Grade \leq 1, then - If resolved in \leq 7 days, then then ↓ 1 dose level. - If resolved in $>$ 7 days, then discontinue study treatment.
Grade 4 (PLT $<$ 25 x 10 ⁹ /L)	Discontinue study treatment.	Discontinue study treatment
Bleeding		
Any bleeding (related to cisplatin or carboplatin) resulting in a transfusion requirement	Omit dose of cisplatin until no further bleeding has been observed. Continuation of study treatment may be considered.	Omit dose of carboplatin until no further bleeding has been observed. Continuation of study treatment may be considered.
INVESTIGATIONS – RENAL		
Serum creatinine		
Grade 1 ($>$ ULN - 1.5 x ULN)	Maintain dose level.	Maintain dose level

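### In Arm B the platinum table and the etoposide section give opposite instructions for severe or slow-to-recover low platelets, and the dose rules disagree on which blood count applies

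*Combined protocol and SAP*

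**What the plan says.** **Platinum (5.3.4.1).** The cisplatin column is headed "Recommended Dose Modifications to cisplatin any time during a cycle of therapy", and the carboplatin column has the same form. In the block that begins "Platelet count decreased (Thrombocytopenia", Grade 4 (below 25,000/mm3) leads to stopping study treatment in both columns. Grade 3 (25,000-50,000/mm3) leads to the same action if it takes more than 7 days to resolve, and to one level down if it resolves sooner. A closing note calls the table general guidance and lets the investigator omit a dose, lower a level or remove the patient.

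**Etoposide (5.3.5.1).** A Grade 4 platelet nadir, with the same 25,000/mm3 threshold, lowers etoposide by one level for the next and all later cycles. All therapy ends only if counts have not recovered in 4 weeks. Separately, under the treatment-day rule, counts that need more than 7 days but no more than 3 weeks to recover lead to resumption at 80 mg/m2.

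**General rules (5.3.1).** Doses follow non-hematologic events and "the lowest ANC and platelet counts during that cycle", referring to the previous cycle. The section also says "If dose reduction is required, reduction is permanent". Its one permission to drop an agent and carry on with the other reads "for Arm A, patients may discontinue one agent due to toxicity and continue the other on-study".

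**Temozolomide (5.3.3).** "Dose reductions for treatment day ANC and platelet counts should also be made according to the Dose Level Table below".

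**Platinum lead-in (5.3.4).** Dose reductions use counts from the treatment day or within 2 days of it, although the table that follows is headed by worst toxicity.

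**The concern.** The two Arm B sections cover the same patient, the same toxicity and, for Grade 4, the same threshold. One ends study treatment; the other gives a further etoposide dose. A site has no rule for choosing between them. What is at stake is patient safety and uniform dosing in severe thrombocytopenia.

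The situation can appear on a scheduled count. Section 8.4.11.1 puts the carboplatin nadir at about day 21, and the blood count for a 21-day cycle is due less than 24 hours before the next cycle (7.1, footnote 3), which is about the same day.

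The second issue is smaller. Section 5.3.1 names one kind of count, 5.3.3 names another, and 5.3.4 and its table name two between them, with no statement of precedence.

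**Working it through.** **1. Reproduce the plan's dose levels.** Etoposide starts at 100 mg/m2 and each level is 20% lower: 100 x 0.8 = 80 and 80 x 0.8 = 64 mg/m2. Both agree with the etoposide table in 5.3.5.

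**2. Set the two Arm B rules side by side.** Assumptions: the patient is on starting doses; each count is both the nadir and the treatment-day count; both recovery criteria are met on the day shown; and 90,000/mm3 is below the laboratory's lower limit of normal.

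| Platelets (/mm3) | Days to recover | Platinum table (5.3.4.1) | Etoposide rules (5.3.5.1) |
|---|---|---|---|
| 20,000 | 5 | stop study treatment | 80 mg/m2 (nadir rule) |
| 20,000 | 10 | stop study treatment | 80 mg/m2 |
| 40,000 | 5 | omit, then one level down | 100 mg/m2 |
| 40,000 | 10 | stop study treatment | 80 mg/m2 |
| 60,000 | 5 | omit, then one level down | 100 mg/m2 |
| 60,000 | 10 | omit, then one level down | 80 mg/m2 |
| 90,000 | 5 | same level | 100 mg/m2 |
| 90,000 | 10 | same level | 80 mg/m2 |

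Stop-versus-continue occurs only for Grade 4, and for Grade 3 lasting more than 7 days. In the other rows the two drugs may move by different amounts, but neither section ends treatment.

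**3. A worked Grade 3 case.** Treatment-day platelets are 40,000, then 70,000 on day 7 and 100,000 on day 10. The platinum table needs Grade 1 or better, which means at least 75,000. Day 7 falls short, so the table says stop. The etoposide rule needs at least 100,000 (and ANC at least 1,500). Assuming the ANC criterion is also met, this is reached on day 10, which is more than 7 days and within 3 weeks, so etoposide resumes at 80 mg/m2.

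**4. Size.** Continuing gives 80 x 3 days = 240 mg/m2 per cycle, against 0 if treatment stops. The full dose would be 100 x 3 = 300 mg/m2, so the continuing patient is 1 - 240/300 = 20% below full dose.

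**5. Does other text settle it?**
- The rule that begins "If different percentages of dose reductions for a specific drug are required because of two different types of toxicities" chooses the larger reduction when two toxicity types compete. Here there is one toxicity, and the choice is between stopping and reducing.
- 5.3.4 holds etoposide with platinum until a decision to skip platinum for that cycle. That coordinates a hold; it does not say what follows an instruction to stop study treatment.
- Where 5.3.4 means platinum alone, it says so, in its rule for recurrent non-hematologic events. The platelet rows refer to study treatment.
- A timing difference does not separate the rules. The case in step 3 uses a treatment-day count, which falls within both the 5.3.4 lead-in and the etoposide rule.

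**6. Which count.** Section 5.3.1 uses the lowest count of the previous cycle; 5.3.3 uses the treatment day; the 5.3.4 lead-in uses the treatment day or within 2 days; the 5.3.4.1 table uses the worst grade at any point in the cycle. Capecitabine's hematologic table (5.3.2.1) gives no timing, so the 5.3.1 sentence may be the only timing rule that drug has.

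**The case against.** The strongest reply is that the platinum table is only recommended and the investigator may depart from it. Stopping would then be the default, with 5.3.5.1 setting the etoposide dose if the investigator continues. That reading is workable, and it softens the contradiction. But the closing note never says that 5.3.5.1 then governs, so the site has to supply the link.

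A second reply is that Arm B agents can be separated. Sections 5.3.4 and 5.3.5 each foresee stopping a single drug for recurrent non-hematologic events, and the Arm A sentence in 5.3.1 follows the third-reduction rule, so it is weak evidence about Arm B. This is fair. It leaves the intended Arm B rule unclear; it does not show that stopping study treatment means stopping platinum alone.

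Third, the events may be uncommon and the safety margin is not trivial. Section 8.3.10 calls cisplatin thrombocytopenia mild and rarely dose-limiting, 8.5.10 calls it uncommon with etoposide, and the day-21 timing applies to carboplatin only. The treatment-day etoposide rule also requires 100,000 platelets before resuming, stricter than the platinum table's 75,000. These points limit the urgency; they do not remove the conflict.

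Two stronger inferences from 5.3.1 are tempting and not supported:
- A reader might carry a recovered nadir of 40,000 into the temozolomide table, where "the dose level -2 will be administered", and conclude that the dose falls from 200 to 128 mg/m2, or 36%. Section 5.3.1 sets no threshold and cannot force a cut by itself. The ordinary reading for temozolomide is the treatment-day count in 5.3.3, and no mid-cycle count is scheduled.
- A reader might see a clash between 5.3.1 and the etoposide rule that leaves the dose unchanged after a nadir neutropenia without fever. Leaving the dose unchanged can simply be one outcome of consulting the nadir.

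**Conclusion.** The concern holds for Arm B platelets in two situations: below 25,000/mm3, and 25,000-50,000/mm3 with more than 7 days to resolve. For a patient on the starting dose, the plan supports both stopping study treatment and continuing etoposide at 240 mg/m2 per cycle, and no text decides between them. This rests on reading study treatment as the whole regimen, which is the natural sense of the words but is not defined.

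The mismatch between 5.3.1, 5.3.3 and the two parts of 5.3.4 over which count applies is also real, but secondary. It is a gap in precedence and carries no demonstrated dose effect.

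The frequency of these cases cannot be derived from the documents. A reader might infer bias in PFS or a loss of power; nothing in the plan allows that to be shown, and it is not claimed. This is a clear wording fault in a safety rule and should be corrected.

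**What to change.** **(a) Platelets in Arm B.** Put one instruction in both 5.3.4.1 and 5.3.5.1 for the two situations above. The default should be the stricter one: discontinue all protocol treatment, with the etoposide text amended to match. If the clinical team confirms that continuing is intended, both sections should instead say one level down for both drugs after full recovery.

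**(b) Which count applies.** Replace the lowest-count sentence in 5.3.1 with a statement that hematologic dose changes follow the drug-specific sections. State in 5.3.4 whether platinum uses treatment-day or worst-in-cycle counts. Before the 5.3.1 sentence is removed, have the clinical team confirm the count timing for capecitabine and write it into 5.3.2.1. That is a clinical decision, because the section now gives none.

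**Cost.** A wording amendment to 5.3.1, 5.3.2.1, 5.3.4, 5.3.4.1 and 5.3.5.1, plus the clinical team's decisions on the points above. The default wording adds no procedure or blood count, and sample size, endpoints and analysis do not change.
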